7. DISCONTINUATION OF STUDY TREATMENT AND PARTICIPANT DISCONTINUATION/WITHDRAWAL

7.1. Discontinuation of Study Treatment

7.1.1. Reasons for Discontinuation

Participants **must** be discontinued from study treatment for the following reasons:

- Consent is withdrawn.
Note: Consent withdrawn means that the participant has explicitly indicated that they do not want to be followed any longer; in this case no further data, except data in public domain, may be solicited from or collected on the participant. Participants may choose to discontinue study treatment and remain in the study to be followed for progression and survival.
- Further participation would be injurious to the participant's health or well-being, in the investigator's medical judgment.
- The participant has an unacceptable toxicity or a toxicity that does not recover in 6 weeks. Investigators who wish to continue treatment after a treatment delay of 4 weeks should consult with the sponsor's medical monitor for approval.
- An AE requiring more than 2 dose reductions of INCB001158.
- The study is terminated by the sponsor.
- The study is terminated by the local health authority, IRB, or IEC.

A participant **may** be discontinued from study treatment as follows:

- If, during the course of the study, a participant is found not to have met eligibility criteria, the medical monitor, in collaboration with the investigator, will determine whether the participant should be withdrawn from study treatment.
- If a participant is noncompliant with study procedures or study treatment administration in the investigator's opinion, the sponsor should be consulted for instruction on handling the participant.

7.1.2. Discontinuation Procedures

In the event that the decision is made to permanently discontinue the study treatment, the EOT visit should be conducted. Reasonable efforts should be made to have the participant return for a follow-up visit. These visits are described in [Table 3](#) and [Table 4](#) (SoA prior and post-crossover respectively), and [Table 5](#) and [Table 6](#) (for laboratory assessments prior and post-crossover respectively). As of Protocol Amendment 3, see only [Table 7](#) for the SoA for all participants.

The last date of the last dose of study treatment and the reason for discontinuation of study treatment will be recorded in the eCRF.

If a participant is discontinued from study treatment:

- The study monitor or sponsor must be notified.
- The reason(s) for withdrawal must be documented in the participant's medical record and the primary reason for withdrawal must be included in the eCRF.
- The EOT visit should be performed.
- The date of the EOT visit should be recorded in the IRT.
- Participants must be followed for safety until the time of the follow-up visit or until study drug-related toxicities resolve, return to baseline, or are deemed irreversible, whichever is longest.

If the participant discontinues study treatment and actively withdraws consent for collection of follow-up data (safety or disease status follow-up), then no additional data collection should occur; however, participants will have the option of withdrawing consent for study treatment but continuing in the follow-up period of the study for safety/efficacy assessments.

NOTE: As of Protocol Amendment 3, no further disease status and survival follow-up assessments will be required beyond the last safety follow-up visit.

7.2. Participant Withdrawal From the Study

A participant may withdraw from the study at any time at his/her own request, or may be withdrawn at any time at the discretion of the investigator for safety, behavioral, compliance, or administrative reasons.

If the participant withdraws consent for disclosure of future information, the sponsor may retain and continue to use any data collected before such a withdrawal of consent.

If a participant withdraws from the study, he/she may request destruction of any samples taken and not tested, and the investigator must document this in the site study records.

See [Table 3](#) and [Table 4](#) (SoA prior and post-crossover respectively), and [Table 5](#) and [Table 6](#) (laboratory assessments prior and post-crossover respectively) for data to be collected at the time of study discontinuation and follow-up and for any further evaluations that need to be completed.

NOTE: As of Protocol Amendment 3, see only [Table 7](#) for the SoA and laboratory assessments for all participants.

7.3. Lost to Follow-Up

A participant will be considered lost to follow-up if he/she repeatedly fails to return for scheduled visits and is unable to be contacted by the study site.

The following actions must be taken if a participant fails to return to the clinic for a required study visit:

- The site must attempt to contact the participant and reschedule the missed visit as soon as possible and counsel the participant on the importance of maintaining the assigned visit schedule and ascertain whether or not the participant wishes to and/or should continue in the study.
- Before a participant is deemed lost to follow-up, the investigator or designee must make every effort to regain contact with the participant (where possible, 3 telephone calls and, if necessary, a certified letter to the participant's last known mailing address or local equivalent methods). These contact attempts should be documented in the participant's medical record.
- Should the participant continue to be unreachable, he/she will be considered to have withdrawn from the study.

8. STUDY ASSESSMENTS AND PROCEDURES

8.1. Administrative and General Procedures

8.1.1. Informed Consent Process

- The investigator or his/her representative will explain the nature of the study to the participant or his/her legally authorized representative and answer all questions regarding the study.
 - Informed consent must be obtained before any study-related procedures are conducted, unless otherwise specified by the Protocol.
 - Informed consent must be obtained using the IRB/IEC-approved version in a language that is native and understandable to the participant. A template will be provided by the sponsor or its designee. The sponsor or its designee must review and acknowledge the site-specific changes to the ICF template. The ICF must include a statement that the sponsor or its designee and regulatory authorities have direct access to participant records.
 - The ICF must contain all required elements and describe the nature, scope, and possible consequences of the study in a form understandable to the study participant.
- Participants must be informed that their participation is voluntary. Participants or their legally authorized representative will be required to sign a statement of informed consent that meets the applicable requirements and regulations for the countries in which the study is being conducted as well as the IRB/IEC or study center.
- The participant must be informed that his/her personal study-related data will be used by the sponsor in accordance with local data protection laws. The level of disclosure must also be explained to the participant.

- The participant must be informed that his/her medical records may be examined by Clinical Quality Assurance auditors or other authorized personnel appointed by the sponsor, by appropriate IRB/IEC members, and by inspectors from regulatory authorities.
- The medical record must include a statement that written informed consent was obtained before the participant was enrolled in the study and the date the written consent was obtained. The authorized person obtaining the informed consent must also sign the ICF.
- Participants must provide consent to the most current version of the ICF(s) during their participation in the study.
- A copy of the ICF(s) must be provided to the participant or the participant's legally authorized representative.

Participants who are rescreened are required to sign a new ICF.

Participants will be told that they are free to refuse to participate and may withdraw their consent at any time and for any reason during the storage period.

8.1.2. Screening Procedures

Screening is the interval between signing the ICF and the day the participant is enrolled in the study (Cycle 1 Day 1). Screening may not exceed 28 days. Assessments that are required to demonstrate eligibility may be performed over the course of 1 or more days during the screening process.

Procedures conducted as part of the participant's routine clinical management (eg, blood count, imaging study) and obtained before signing of informed consent may be used for screening or baseline purposes provided the procedure meets the Protocol-defined criteria and has been performed in the timeframe of the study (ie, within 28 days of Cycle 1 Day 1). For participants who are enrolled in the study, information associated with eligibility requirements must be entered into the appropriate eCRF pages.

Results from the screening visit evaluations will be reviewed to confirm eligibility before enrollment or the administration of study drug. Tests with results that fail eligibility requirements may be repeated once during screening if the investigator believes the results to be in error. For screening assessments that are repeated, the most recent available result before treatment assignment will be used to determine eligibility. Additionally, a participant who fails screening may repeat the screening process 1 time if the investigator believes there has been a change in eligibility status (eg, after recovery from an infection).

See Sections [5.4](#) and [5.5](#) for information regarding screen failures and replacement of participants, respectively.

8.1.3. Interactive Response Technology Procedure

Each participant will be identified in the study by a participant ID number, which is a combination of the site ID and participant number. Site staff should contact the IRT system to obtain the participant ID number during screening. Upon determining that the participant is

eligible for study entry, the IRT will be contacted to obtain the treatment assignment. Additionally, the IRT system will be contacted at each regular study visit to update the study drug supply. Additional details are provided in the IRT Manual.

8.1.4. Distribution of Reminder Cards and Diaries

Participants will be provided with a reminder card at each visit. The reminder card will indicate the date/time of the next visit and will also remind the participant that they should not take their morning dose of INCB001158 before visiting the clinic on those days, as they will take them after blood draws for safety evaluation have been completed.

Participants will also be provided with diaries to record dates, times, and doses of INCB001158 that they take between clinic visits.

8.1.5. Demography and Medical History

8.1.5.1. Demographics and General Medical History

Demographic data and general medical history will be collected at screening by the investigator or qualified designee and will include year of birth/age, race, ethnicity, medical and surgical history, and current illnesses. Medical history will include relevant medical or surgical treatment within the last 10 years that are considered to be clinically significant by the investigator.

8.1.5.2. Disease Characteristics and Treatment History

A disease-targeted medical and treatment history will be collected at screening. Details regarding the participant's malignancy under study, including date of diagnosis, initial and current cancer stage, tumor histology, and relevant disease characteristics, and prior treatments, including systemic treatments, radiation, and surgical procedures, will be recorded.

8.2. Efficacy Assessments

NOTE: As of Protocol Amendment 3, the disease assessments are only required to be performed as per the site standard of care guidelines for the participant's condition and monitoring.

Participants must be withdrawn from the study if, in the opinion of the investigator, the disease has progressed and the participant is no longer having clinical benefit from the study treatment.

8.2.1. Evaluations

8.2.1.1. Responses Categories

Assessment of tumor response and disease progression will be conducted in accordance with the IMWG response criteria. Disease evaluations will include measurements of myeloma proteins, bone marrow examinations, skeletal surveys, assessment of extramedullary plasmacytomas, and measurements of serum calcium corrected for albumin.

Efficacy/disease evaluations must be performed at each treatment cycle as specified in the SoA (see [Table 3](#) and [Table 4](#); as of Protocol Amendment 3, see [Table 7](#) for all participants). The sponsor may request that the disease assessments be sent for central independent review. Disease evaluations scheduled for treatment days should be collected before study treatment is administered. Disease evaluations will be performed by a central laboratory (unless otherwise

specified) until disease progression or the EOT. This study will use the IMWG consensus recommendations for MM treatment response criteria (Durie et al 2006, Kumar et al 2016, Rajkumar et al 2011) presented in [Table 19](#). Per IMWG uniform response criteria, all response categories and PD require 2 consecutive assessments except for radiographic or bone marrow assessments. For quantitative Ig at baseline, M-protein, IFE, and FLC measurements in serum and 24-hour urine, the investigator will use results provided by the central laboratory. For participants with suspected daratumumab interference on SPEP and IFE, a reflex assay will be performed (see [Appendix E](#)). Participants with confirmed daratumumab interference who meet all other clinical criteria for CR or sCR will be considered CR/sCR.

Table 19: International Uniform Response Criteria Consensus Recommendations

Response	Response Criteria
Stringent complete response (sCR)	
• CR as defined below, plus• Normal FLC ratio, and• Absence of clonal PCs by immunohistochemistry, immunofluorescence,^a or 2- to 4-color flow cytometry.
Complete response (CR) ^b	
• Negative immunofixation on the serum and urine, and• Disappearance of any soft tissue plasmacytomas, and• < 5% PCs in bone marrow.
Very good partial response (VGPR) ^b	
• Serum and urine M-component detectable by immunofixation but not on electrophoresis, or• ≥ 90% reduction in serum M-protein plus urine M-protein < 100 mg/24 hours.
Partial response (PR)	
• ≥ 50% reduction of serum M-protein and reduction in 24-hour urinary M-protein by ≥ 90% or to < 200 mg/24 hours.• If the serum and urine M-protein are not measurable, a decrease of ≥ 50% in the difference between involved and uninvolved FLC levels is required in place of the M-protein criteria.• If serum and urine M-protein are not measurable, and serum free light assay is also not measurable, ≥ 50% reduction in bone marrow PCs is required in place of M-protein, provided baseline bone marrow plasma cell percentage was ≥ 30%.• In addition to the above criteria, if present at baseline, a ≥ 50% reduction in the size (SPD) of soft tissue plasmacytomas is also required.
Minimal response (MR)	
• ≥ 25% but ≤ 49% reduction of serum M-protein and reduction in 24-hour urine M-protein by 50% to 89%.• In addition to the above criteria, if present at baseline, 25% to 49% reduction in the size of soft tissue plasmacytomas is also required.• No increase in size or number of lytic bone lesions (development of compression fracture does not exclude response).
Stable disease (SD)	
• Not meeting criteria for CR, VGPR, PR, MR, or PD.

Table 19: International Uniform Response Criteria Consensus Recommendations (Continued)

Response	Response Criteria
Progressive disease (PD) ^c	
Increase of 25% from lowest response value in any one of the following:
 
 • Serum M-component (absolute increase must be ≥ 0.5 g/dL), • Urine M-component (absolute increase must be ≥ 200 mg/24 hours), • Only in participants without measurable serum and urine M-protein levels: the difference between involved and uninvolved FLC levels (absolute increase must be > 10 mg/dL). • Only in participants without measurable serum and urine M-protein levels and without measurable disease by FLC levels, bone marrow PC percentage (absolute percentage must be $\geq 10\%$). • Bone marrow plasma cell percentage: the absolute percentage must be $> 10\%$. • Definite development of new bone lesions or soft tissue plasmacytomas or definite increase in the size of existing bone lesions or soft tissue plasmacytomas (SPD). • Development of hypercalcemia (corrected serum calcium > 11.5 mg/dL) that can be attributed solely to the PC proliferative disorder.

FLC = free light chain; PC = plasma cell; SPD = sum of the products of the maximal perpendicular diameters of measured lesions.

Note: All response categories (CR, sCR, VGPR, PR, and PD) require 2 consecutive assessments made at any time before the institution of any new therapy; CR, sCR, VGPR, PR, and SD categories also require no known evidence of progressive or new bone lesions if radiographic studies were performed. VGPR and CR categories require serum and urine studies regardless of whether disease at baseline was measurable on serum, urine, both, or neither.

Note: Radiographic studies are not required to satisfy these response requirements. Bone marrow assessments need not be confirmed. For PD, serum M-component increases of more than or equal to 1 g/dL are sufficient to define relapse if starting M-component is ≥ 5 g/dL.

^a Presence/absence of clonal cells is based upon the kappa/lambda ratio. An abnormal kappa/lambda ratio by immunohistochemistry or immunofluorescence requires a minimum of 100 plasma cells for analysis. An abnormal ratio reflecting presence of an abnormal clone is kappa/lambda of $> 4:1$ or $< 1:2$.

^b Clarifications to IMWG criteria for coding CR and VGPR in participants in whom the only measurable disease is by serum FLC levels: CR in such participants indicates a normal FLC ratio of 0.26 to 1.65 in addition to CR criteria listed above. VGPR in such participants requires a $> 90\%$ decrease in the difference between involved and uninvolved FLC levels.

^c Clarifications to IMWG criteria for coding PD: Bone marrow criteria for PD are to be used only in participants without measurable disease by M-protein and by FLC levels; "25% increase" refers to M-protein, FLC, and bone marrow results, and does not refer to bone lesions, soft tissue plasmacytomas, or hypercalcemia, and the "lowest response value" does not need to be a confirmed value.

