8.2.1.8. Assessment of Extramedullary Plasmacytomas

Sites of known extramedullary plasmacytomas must be documented during the screening period. Clinical examination or MRI may be used to document extramedullary sites of disease. Computed tomography scan evaluations are an acceptable alternative if there is no contraindication to the use of IV contrast. Positron emission tomography scan alone (ie, without a CT) or ultrasound tests are not acceptable to document the size of extramedullary plasmacytomas.

Extramedullary plasmacytomas should be assessed for all participants with a history of plasmacytomas or if clinically indicated at screening, by clinical examination or radiologic imaging. For participants with a history of plasmacytomas assessed by physical examination, physical examination should be repeated on Cycle 1 Day 1 if not done within 14 days before administration of study treatment. Assessment of measurable sites of extramedullary disease will be performed and evaluated locally approximately every 4 weeks by physical examination or approximately every 12 weeks by imaging (if required) for participants with a history of

plasmacytomas or as clinically indicated during treatment for other participants, until development of confirmed CR or confirmed disease progression. For every participant, the methodology used for evaluation of each disease site should be consistent across all visits. Irradiated or excised lesions will be considered not measurable and will be monitored only for disease progression.

To qualify for PR, the sum of products of the perpendicular diameters of the existing extramedullary plasmacytomas must have decreased by at least 50%, and new plasmacytomas must not have developed (see the disease response criteria in [Table 19](#)). To qualify for disease progression, either the sum of products of the perpendicular diameters of the existing extramedullary plasmacytomas must have increased by at least 50% or a new plasmacytoma must have developed. In the cases where not all existing extramedullary plasmacytomas are reported, but the sum of products of the perpendicular diameters of the reported plasmacytomas have increased by at least 50%, this will also qualify as disease progression.

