10.4. Statistical Analyses

10.4.1. Efficacy Analyses

10.4.1.1. Primary Efficacy Analyses

The primary endpoint of the Phase 2 portion of the Protocol is ORR, defined as the proportion of participants with CR, VGPR, or PR, according to IMWG Criteria in the randomized IMWG response evaluable population. Participants will be summarized by treatment group assignment in Phase 2.

The primary analysis of ORR in Phase 2 will compare Treatment Groups A and B modeling the ORR of each treatment group with a Beta (0.5,0.5) prior, calculating the probability that the posterior distribution of the ORR for Treatment Group A exceeds that of the posterior distribution the ORR for Treatment Group B. If $x_1 (n_1)$ is the number of responders (evaluable participants) in Treatment Group A and $x_2 (n_2)$ correspond to the same for Treatment Group B, the resulting posterior distribution will be

$$f_i(\gamma_i | x_i, n_i) = \frac{\Gamma(n_i + 1)}{\Gamma(x_i + 0.5)\Gamma(n_i + 0.5 - x_i)} \gamma_i^{x_i + 0.5} (1 - \gamma_i)^{n_i + 0.5 - x_i}$$

The resulting probability that the ORR for Treatment Group A exceeds that of Treatment Group B, that is, the PPoS, is the quantity

$$\text{PPoS} = \Pr(\text{ORR}_A > \text{ORR}_B | x_1, n_1, x_2, n_2) = \int_0^1 \int_{\gamma_2}^1 f_1(\gamma_1 | x_1, n_1) f_2(\gamma_2 | x_2, n_2) d\gamma_1 d\gamma_2$$

Objective response rate and its 90% Bayesian credible intervals for each treatment group will be presented.

Interim analyses will be conducted after the 31st participant is randomized and after each subsequent participant is to be randomized to adjust the randomization rate between Treatment Groups A and B and to determine whether the study should be terminated for positive efficacy. See Section 10.5.2.1 for details on the conduct of these interim analyses.

If the study does not terminate for early efficacy, the final analysis will take place once all participants have been randomized and monitored for response for 3 months OR once all participants have discontinued the study. If $\text{PPoS} > 0.915$, then the null hypothesis will be rejected, and Treatment Group A will be considered to be superior (with respect to ORR) to Treatment Group B.

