7.3. Analysis of the Efficacy Parameters

7.3.1. Primary Efficacy Analysis

Objective response rate is defined as the proportion of participants with at least 1 confirmed response of CR, VGPR, or PR, according to IMWG criteria.

Objective response rate in Phase 2 was the planned primary endpoint. Due to the small number of participants in Phase 2, only listings of the response assessment data will be provided. Therefore, ORR will not be calculated and will not be presented in the CSR.

The IMWG criteria are presented in [Table 2](#). Per IMWG uniform response criteria, all response categories and PD require 2 consecutive assessments except for radiographic or bone marrow assessments. If a participant discontinues treatment without a PD, receives a subsequent anticancer therapy and then responds, this will not be included as a responder for ORR.

Table 2: International Uniform Response Criteria Consensus Recommendations

Response	Response Criteria
sCR	
• CR as defined below, plus• Normal FLC ratio, and• Absence of clonal PCs by immunohistochemistry, immunofluorescence,^a or 2- to 4-color flow cytometry
CR ^b	
• Negative immunofixation on the serum and urine, and• Disappearance of any soft tissue plasmacytomas, and• < 5% PCs in bone marrow
VGPR ^b	
• Serum and urine M-component detectable by immunofixation but not on electrophoresis, or• ≥ 90% reduction in serum M-protein plus urine M-protein < 100 mg/24 hours

Table 2: International Uniform Response Criteria Consensus Recommendations (Continued)

Response	Response Criteria
PR	
 • $\geq 50\%$ reduction of serum M-protein and reduction in 24-hour urinary M-protein by $\geq 90\%$ or to $< 200 \text{ mg/24 hours}$ • If the serum and urine M-protein are not measurable, a decrease of $\geq 50\%$ in the difference between involved and uninvolved FLC levels is required in place of the M-protein criteria • If serum and urine M-protein are not measurable, and serum free light assay is also not measurable, $\geq 50\%$ reduction in bone marrow PCs is required in place of M-protein, provided baseline bone marrow PC percentage was $\geq 30\%$ • In addition to the above criteria, if present at baseline, a $\geq 50\%$ reduction in the size (SPD) of soft tissue plasmacytomas is also required

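### VGPR carries no plasmacytoma condition although CR, PR and MR do, so a participant can fail PR on lesion size, be graded VGPR and meet the ORR definition

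*Protocol*

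**What the plan says.** Protocol Section 8.2.1.1, Table 19, sets the response categories, and SAP Section 7.3.1, Table 2, repeats them. Three categories deal with soft tissue plasmacytomas:

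- CR needs "Disappearance of any soft tissue plasmacytomas".
- PR adds that "if present at baseline, a ≥ 50% reduction in the size (SPD) of soft tissue plasmacytomas is also required".
- MR adds that, if lesions were present at baseline, a "25% to 49% reduction in the size of soft tissue plasmacytomas is also required".

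VGPR ranks between PR and CR and has two routes. One is "Serum and urine M-component detectable by immunofixation but not on electrophoresis, or" the other, which is "≥ 90% reduction in serum M-protein plus urine M-protein < 100 mg/24 hours". Footnote b adds a rule for FLC-only disease (a fall of more than 90% in the FLC difference). The table notes add conditions on bone lesions and on serum and urine studies. None of these mentions plasmacytoma size for VGPR.

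Protocol Section 8.2.1.8 gives its shrinkage rule for one category: "To qualify for PR, the sum of products of the perpendicular diameters of the existing extramedullary plasmacytomas must have decreased by at least 50" percent. It also covers progression but does not mention VGPR.

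Protocol Section 10.4.1.1 defines the primary endpoint as "the proportion of participants with CR, VGPR, or PR, according to IMWG Criteria". The objectives tables (Protocol Table 8, SAP Table 1) define it as a documented response of PR or better.

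**The concern.** A higher response category should not be easier to reach on one disease component than the category below it. Here it is. The table shows that its authors nest categories explicitly when they intend to, because sCR is written as CR plus further items. VGPR is not written as PR plus further items.

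VGPR counts toward ORR. The gap therefore sits in the responder definition for the planned Phase 2 primary analysis, for the posterior probability (PPoS) that drives adaptive randomization and early stopping, and for TTR and DOR, which both start from a PR, VGPR or CR. Protocol Section 6.3 bases the randomization updates on investigator assessment, so two sites could grade the same participant differently.

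**Working it through.** **Step 1: the conditions side by side** (Protocol Table 19 and notes; SAP Table 2 is the same).

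| Category | M-protein, immunofixation or FLC | Plasmacytoma, if present at baseline | In ORR? |
|---|---|---|---|
| CR | negative serum and urine immunofixation | must disappear | yes |
| VGPR | immunofixation only, or serum fall ≥ 90% with urine < 100 mg/24 h, or FLC difference down > 90% | none stated | yes |
| PR | serum fall ≥ 50% with urine fall ≥ 90% or to < 200 mg/24 h (FLC or marrow alternatives) | SPD fall ≥ 50% | yes |
| MR | serum fall 25% to 49%, urine fall 50% to 89% | fall of 25% to 49% | no |

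**Step 2: apply the rules to two hypothetical participants**, each with a baseline plasmacytoma whose SPD has fallen 20% and with urine M-protein below 100 mg/24 h.

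- Serum M-protein down 92%: CR fails (lesion present), VGPR is met, PR fails (20% < 50%). Graded VGPR, so a responder.
- Serum M-protein down 80%: VGPR fails (80% < 90%, assuming M-protein is still visible on electrophoresis), PR fails on the lesion, and MR fails because 80% is above its 49% ceiling. Graded SD, so a non-responder.

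The lesion is the same. It blocks a response in the second participant and has no bearing in the first.

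**Step 3: limits of the gap.** The participant must meet a VGPR criterion on M-protein, electrophoresis or FLC. In Table 19 a new or definitely enlarged plasmacytoma is PD. What is left is a stable or under-50%-shrunk lesion alongside a deep M-protein or FLC response.

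**Step 4: reproduce the plan's own figures.** Inputs are from Protocol Sections 10.1.2, 10.4.1.1 and 10.5.2.1: 30 participants at 1:1:1, then up to 50 to A or B with assignment probability equal to PPoS limited to 0.2–0.8; Beta(0.5, 0.5) priors; 4 participants per month; response known after 3 months; early stop at PPoS > 0.9975; final success at PPoS > 0.915. PPoS is Pr(p_A > p_B) with independent posteriors Beta(x + 0.5, n − x + 0.5). There were 40,000 replications.

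| A vs B | Table 26 rejection | Simulated |
|---|---|---|
| 20% vs 20% | 9.8% | 9.7% |
| 35% vs 20% | 50.1% | 49.9% |
| 40% vs 20% | 65.7% | 65.5% |
| 45% vs 20% | 78.7% | 78.8% |

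The standard error under the null is √(0.098 × 0.902 / 40,000) = 0.15 point, so the design is reproduced.

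**Step 5: sensitivity on an assumption the documents do not supply.** Let a fraction f of true non-responders in both groups be counted as responders through the gap. The apparent rate is p + f(1 − p).

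| f | Apparent A (true 45%) | Apparent B (true 20%) | Power | Rejection when both are truly 20% |
|---|---|---|---|---|
| 0 | 45.0% | 20.0% | 78.8% | 9.7% |
| 1% | 45.55% | 20.8% | 77.8% | 9.8% |
| 2% | 46.1% | 21.6% | 76.6% | 9.8% |
| 5% | 47.75% | 24.0% | 73.6% | 9.8% |
| 10% | 50.5% | 28.0% | 69.3% | 9.9% |

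At f = 10% the difference shrinks from 25 to 50.5 − 28.0 = 22.5 points.

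**Step 6: one participant.** With Table 26 expected Group A sizes of 34.7 to 41.5, one regraded participant moves ORR by 1/41.5 = 2.4 to 1/34.7 = 2.9 points. In a chosen boundary case, 15/41 versus 4/21 gives PPoS 0.924 and 14/41 versus 4/21 gives 0.894, on either side of 0.915.

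**The case against.** Four points can fairly be made against this.

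- *The main use of ORR has gone.* This stands. Amendment 3 records that enrollment was terminated. SAP Section 7.3.1 says ORR will not be calculated or presented, and SAP Section 9 says no formal interim analysis will be performed. A reader might infer from Steps 5 and 6 that a reported ORR or a superiority decision is distorted. No such result will be produced.
- *The gap is narrow.* This also stands. A reader might infer that anyone failing PR on lesion size becomes VGPR, or that growing lesions count as responses. Neither follows: the VGPR M-protein or FLC criterion must be met, and Table 19 makes definite enlargement PD. Section 8.2.1.8 sets progression by size at an SPD rise of at least 50%, or a new lesion. Growth below that figure is a separate point of wording and is not relied on here.
- *The size is unknown.* This stands. Assuming that 10% to 20% of participants have plasmacytomas and 10% to 30% of those are discordant gives 1 to 6 points of ORR, but neither share is in the documents. The upper end fits poorly with a planned Group B response rate of 20%. The PPoS flip is a boundary case, and any single change at a threshold would do the same. A reader might also infer more false superiority claims; with equal discordance Type I error stays at about 10%.
- *Response of PR or better implies that VGPR presupposes PR, and Table 19 only presents cited criteria.* This stands in part. The ordered reading is natural, and the cited publications cannot be consulted here. But neither document states the nesting, and the table is what sites and programmers apply.

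**Conclusion.** The point holds as an internal inconsistency in the response rules. As written, a participant with a baseline plasmacytoma that is stable or has shrunk by less than 50%, and who meets the VGPR M-protein or FLC criterion, fails PR but is VGPR and meets the ORR definition.

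For the protocol's planned analysis, the consequence under equal discordance is a loss of power: 1.0 point at f = 1%, 2.2 at 2%, 5.2 at 5% and 9.5 at 10%. Type I error does not rise. These figures rest on an assumed f that is the same in both groups; unequal discordance would act on the contrast itself, and the documents give no basis for sizing it.

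Under the current SAP the effect is confined to the per-participant listings of best overall response, TTR and DOR (SAP Sections 7.3.2.1 to 7.3.2.3; Listings 2.6.1 and 2.6.2). It is worth correcting because those listings are the only efficacy output for these endpoints, but it does not bear on any planned test.

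**What to change.** After checking the cited response criteria, reconcile VGPR with PR in three places: Protocol Table 19, SAP Table 2 and Protocol Section 8.2.1.8. State that a VGPR counts as a response only if the PR plasmacytoma condition (SPD reduction of at least 50% if lesions were present at baseline) is also met. Say as well how a participant who fails only that condition is graded. By the letter of the current table the result would be SD, because the MR row stops at a 49% serum fall.

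Then re-check the listed best overall response, TTR and DOR for participants with baseline plasmacytomas, using the SPD data available, and record any change.

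The cost is a sentence or two in each place and a review of a small subset. No new assessments are needed, but matched SPD may be missing: imaging was planned about every 12 weeks, and since Amendment 3 disease assessments follow standard of care. The downside is that a few responses may be downgraded, or left unconfirmed where no matched measurement exists.
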